4.1 Background- Atrial Fibrillation (AF) and Clinical Need

Atrial Fibrillation (AF) is the most common clinically-significant cardiac arrhythmia. It is a major public health concern in the United States, affecting an estimated 2.3 million people in North America and 4.5 million people in Europe. ^[1] It has been projected that the prevalence of AF will increase 2.5 fold during the next 50 years in the United States. ^[2] AF is associated with increased cardiovascular morbidity and mortality and the prevalence increases over time due to the aging population and an increase in age-specific occurrence of AF. ^[3] ^[4] ^[5]

Symptoms of AF vary with the ventricular rate, underlying functional status, duration of AF, presence and degree of structural heart disease, and individual patient perception; however, most patients with AF complain of palpitations, angina, dyspnea, fatigue, or dizziness. AF also significantly impairs quality of life, with up to two-thirds of patients reporting it is disruptive and debilitating to their lives. ^[6] ^[7] ^[8] AF is an abnormal heart rhythm that has been classified as recurrent when two or more episodes are detected. If these episodes of AF last less than seven days and terminate spontaneously, then it is classified as paroxysmal AF (PAF). PAF accounts for approximately 40 to 45 percent of AF cases. ^[4] ^[9] Episodes of AF that are continuous and sustained beyond 7 days but less than 12 months are classified as persistent AF (PeAF) according to the most recent 2017 HRS/EHRA Consensus Statement. Long-standing persistent AF is defined as continuous AF of greater than 12 months duration. ^[10]

AF is a sustained arrhythmia characterized by rapid and disorganized atrial activation leading to impaired atrial function, which can be diagnosed on an ECG by lack of a P-wave and irregular QRS complexes. The disorganized atrial activation appears as “fibrillatory” waves activating the atria at a rate generally between 350 and 600 beats/min and the syncytial contraction of the atria is replaced by irregular atrial twitches. While AF can occur in isolation, it may also be associated with other arrhythmias such as Atrial Flutter or Atrial Tachycardia.

The electrophysiological mechanisms responsible for AF may include rapid focal tachyarrhythmia in the pulmonary veins (PVs) and/or other atrial regions with fibrillatory conduction, multiple reentrant wavelet conduction initiated by premature atrial complexes (PACs) and/or atrial tachyarrhythmia, and/or formation of stable or unstable reentrant circuits of very short cycle lengths that generate fibrillatory conduction. ^[11] ^[12]

Of all electrophysiological mechanisms responsible for AF, of significant interest are the PVs which have been identified to play a critical role in triggering and maintaining AF. Haissaguerre and colleagues have demonstrated that in most AF patients, the focus is in one of the PVs. ^[13]

4.1.1 Prior Clinical Evidence for RF Ablation to Treat Persistent AF

Catheter ablation is commonly performed for persistent AF (PeAF), but few high quality randomized controlled trials (RCTs) exist. ^[17] Multiple RF catheters have been approved for the treatment of paroxysmal Atrial Fibrillation, but to date there are no RF catheters approved in the United States specifically for the treatment of PeAF.

Following the approval of RF catheters for PAF, companies are now seeking approval for PeAF. Biosense-Webster is currently enrolling subjects in the PRECEPT study (NCT#02817776) to demonstrate safety and effectiveness of the THERMOCOOL SMARTTOUCH® SF Catheter in the treatment of drug refractory, symptomatic persistent Atrial Fibrillation.

The optimal RF lesion set to treat PeAF is a controversial topic, but as demonstrated in a large RCT study, STAR-AF II (NCT#01203748), it was shown that PVI only may be as effective as other additional ablation strategies. STAR-AF II randomly assigned 589 participants with PeAF in a 1:4:4 ratio to a) ablation with PVI only (67 patients), b) PVI plus ablation of electrograms (egm) showing complex fractionated activity (263 patients) or c) PVI plus additional linear ablation across the atrial roof and mitral isthmus (259 patients)^[18]. While there was a greater percentage of patients with no recurrent PeAF at 18 months in the PVI only group (59% vs. 49% and 46%, for the PVI plus complex fractionated egm or linear ablation, respectively) the study found that there was no reduction in the freedom from PeAF based on study ablation strategies.

The DiamondTemp Ablation System was being evaluated in the DIAMOND-AF Study for the treatment of drug refractory, symptomatic paroxysmal Atrial Fibrillation (NCT#03334630). DIAMOND-AF was a global, multi-center, randomized clinical study to evaluate the DiamondTemp System in 480 subjects with paroxysmal Atrial Fibrillation. The DIAMOND-AF study enrollment was completed in 2018.

The Sponsor is initiating a study to pursue a US indication to demonstrate the safety and effectiveness of the DiamondTemp Ablation System for the treatment of persistent AF. The study will focus on PVI being the “cornerstone” of PeAF ablation but will allow physicians to consider additional ablation strategies per their standard ablation practice and within the recommendations of the protocol.

The DiamondTemp Ablation System is designed to give operators direct measures of lesion creation (i.e. tissue - tip interface temperatures and local electrograms recordings that attenuate during ablation and lesion formation). The DiamondTemp Catheter design, materials and composite tip geometry allow for the recording of local electrograms at the ablation site. Six thermocouples at the DiamondTemp Catheter tip provide surface temperature feedback. The DiamondTemp Generator modulates power to maintain the catheter-tissue interface temperature at a pre-defined set point optimal for creating an effective lesion. These features may prove to be beneficial in creating safe and effective RF ablation for the treatment of PeAF.

4.1.2 Summary Of First-In-Human Clinical Study (TRAC-AF)

Epix Therapeutics conducted a multi-center First-In-Human clinical study, TRAC-AF, to establish evidence of clinical safety and effectiveness of the DiamondTemp Ablation System to treat patients with drug refractory, recurrent, symptomatic paroxysmal Atrial Fibrillation (PAF).

TRAC-AF (DiamondTemp TempeRAture-Controlled and Contact Sensing RF Ablation Clinical Trial for Atrial Fibrillation, NCT#02821351) study was a prospective, multi-center, single-arm feasibility study initiated in 2016 and conducted at four European investigational sites.

Enrollment was conducted in two phases. Phase 1 included enrollment of 38 subjects from January through March of 2016; Phase 2 included enrollment of an additional 34 subjects from June through July

2017. A total of 72 subjects were enrolled in the study and 70 subjects were treated with the study device and analyzed. Enrollment is now closed and all subjects in both phases have completed 12-month follow-up visits and are now exited from the study.

All primary study endpoints have been met through 30 days follow up. Assessments of primary safety events resulted in two (2) SAEs (2.9%) through the 7-day safety endpoint and three (3) SAEs (4.3%) through the 30-day safety endpoint. The primary effectiveness endpoint of acute procedural success was achieved in 100% of subjects. Freedom from AF at 12 months post-procedure was 72.5%.

4.1.3 TRAC-AF Study Design

Subjects with symptomatic PAF who were refractory or intolerant to at least 1 anti-arrhythmic drug (AAD; class I-IV) were screened for enrollment. Subjects that met the study eligibility criteria and signed the informed consent form (ICF) were enrolled and treated in accordance with the protocol and the HRS/EHRA/ECAS Expert Consensus Statement on Catheter and Surgical Ablation of Atrial Fibrillation. ^[14] ^[10] Subjects received ablation using the investigational device which required electrical isolation of all clinically relevant pulmonary veins.

4.1.4 TRAC-AF Investigational Device

The TRAC-AF investigational device was the DiamondTemp Ablation System. The investigational device was used with a commonly available EP recording system, cardiac stimulator and mapping device, the St. Jude EnSite Velocity or Precision Cardiac Mapping System. There were no control devices in the study.

4.1.5 TRAC-AF Clinical Endpoints

Primary Safety Endpoint: The safety of the DiamondTemp Ablation System was assessed by evaluating the nature and frequency of serious adverse events (SAEs) and serious adverse device effects (SADEs) during the time of the ablation procedure and within 7 days afterwards.

Long Term Primary Safety: The long-term safety of the DiamondTemp Ablation System was assessed by evaluating the nature and frequency of SAEs and SADEs at 30 days post-procedure.

Primary Effectiveness Endpoint: The effectiveness of the DiamondTemp Ablation System was evaluated post-ablation by demonstration of acute procedural success, defined as isolation of clinically-relevant pulmonary veins by demonstration of block or isolation of signals, confirmed after delivery of the ablation treatment.

Secondary Endpoints: The chronic safety of the DiamondTemp Ablation System was assessed by evaluating the nature and frequency of adverse events (AE) and adverse device effects (ADE) at 90 days, 6 months and 12 months post-procedure.

4.1.6 Study Eligibility Criteria

Subjects presenting with drug refractory, paroxysmal Atrial Fibrillation requiring treatment and clinically indicated for standard of care pulmonary vein isolation ablation treatment were eligible for screening and potential enrollment in the study. Enrollment was confirmed once the subject signed informed

consent, had echocardiographic assessment to confirm final eligibility and the study device was introduced into the subject's vasculature.

Subjects had to meet all of the defined inclusion and none of the defined exclusion criteria to be eligible for enrollment in this study.

Inclusion Criteria

1. Suitable candidate for intra-cardiac mapping and ablation for arrhythmias.
2. History of recurrent symptomatic PAF with ≥ 2 episodes reported within the 365 days (12 months prior to enrollment.
3. At least 1 episode of AF documented by Holter monitor, rhythm strip, trans-telephonic monitor (TTM), or 12-lead ECG prior to enrollment.
4. Refractory to at least one Class I-IV anti-arrhythmic drug (AAD).
5. Eighteen (18) years of age or above.

Exclusion Criteria

1. Previous left atrial ablation procedure
2. Intracardiac thrombus, tumor or other abnormality that precludes catheter introduction and placement
3. Known severe cerebrovascular disease or history of cerebrovascular event (within 1 month)
4. Subjects with severely impaired kidney function as measured by a Cockcroft-Gault Glomerular Filtration Rate (GFR) 3 with a GFR ≤ 29 .
5. Active gastrointestinal bleeding
6. Active infection or fever ($>100.5^{\circ}\text{F}/38^{\circ}\text{C}$)
7. Sepsis
8. Cardiac surgery within the past two months.
9. Short life expectancy (<1 yr.) due to other illnesses, such as cancer or pulmonary, hepatic, or renal disease Significant anemia (hemoglobin < 8.0 mg/dL)
10. Severe uncontrolled systemic hypertension (systolic pressure > 240 mm Hg within the last 30 days)
11. Documented anaphylaxis during previous exposure to angiographic contrast media
12. Uncontrolled congestive heart failure (NYHA1 Class III or IV)
13. Unstable angina or acute myocardial infarction within the past three months
14. Bleeding, clotting disorders, or known thrombosis
15. Severe Peripheral vascular disease
16. Uncontrolled diabetes
17. Heart valve replacement
18. Mitral clip (E-valve)
19. Women who are of childbearing potential who are currently pregnant or not willing to use contraception for the duration of the study
20. Active participation in another investigational protocol currently or the last 30 days
21. Unable or unwilling to take anti-coagulants
22. Unwilling or unable to comply with any protocol or follow up requirements

4.1.7 Study Results

Study Accountability and Disposition

Study enrollment in TRAC-AF is closed and all subjects in both phases have completed their 12-month follow-up visits and are now exited from the study. Subjects were followed for 7 and 30 days after the index ablation procedure to assess primary safety and effectiveness endpoints. Table 1 provides a summary of the subject disposition for the study. Although a total of seventy-two (72) subjects met the definition for enrollment, analysis of the study results was conducted on seventy (70 subjects).

Table 1. Subject Accountability and Disposition

Subject Accountability	Number
Subjects enrolled in study	72
Subjects who did not have PVI attempted with study device (excluded from the analysis)	2
Analyzable Population	70

Baseline subject demographics for the analyzable subjects are described in Table 2. The mean age for subjects in this cohort was 60.5 ± 9.8 years, with a higher incidence of subjects being of males (N=42) vs. females (N=28). Overall the characteristics of the subjects enrolled in the study were representative of the patient population usually undergoing RF ablation for the treatment of paroxysmal Atrial Fibrillation.

Study Population Demographics

Table 2. Subject Demographics (n=70)

Characteristic	Measurement	Results	
Age at Ablation Procedure (years)	Mean \pm SD	60.5	\pm 9.8
	Range	35	- 76
Gender [N] (%)	Female	28	(40%)
	Male	42	(60%)
Height (cm)	Mean \pm SD	173.8	\pm 11.7
	Range	115.0	- 194.0
Weight (kg)	Mean \pm SD	91.3	\pm 17.5
	Range	59.0	- 140.0
Resting Heart Rate (bpm)	Mean \pm SD	72.2	\pm 17.6
	Range	47.0	- 135.0
Resting Systolic BP (mmHg)	Mean \pm SD	142.5	\pm 17.6
	Range	110.0	- 135.0
Resting Diastolic BP (mmHg)	Mean \pm SD	82.6	\pm 10.1
	Range	60.0	- 110.0
Hemoglobin (g/l)	Mean \pm SD	140.0	\pm 33.5
	Range	13.1	- 176.0
Creatinine (umol/l)	Mean \pm SD	88.5	\pm 17.8
	Range	54.0	- 140.1
GFR (ml/min/1.73m ²)	Mean \pm SD	77.1	\pm 19.0
	Range	34.0	- 128.0

LVEF % ⁱ	Mean \pm SD	61.2%	\pm	7.2%
	Range	25.0%	-	72.0%
LA diameter, cm ⁱⁱ	Mean \pm SD	4.4	\pm	0.7
	Range	2.9	-	6.5

i LVEF not recorded on four subjects

ii LA diameter not recorded on 14 subjects

The medical history of each subject was assessed including history of Atrial Fibrillation, cardiovascular disease, non-cardiovascular disease and cardiac surgery at time of the screening visit. Table 3 lists the pre-existing conditions recorded during the screening visits.

Table 3. Medical History, (N=70)

PAF History	N (%)
History of Prior Ablation Treatment	0 (0)
Refractory to Anti-Arrhythmic Drugs	70 (100)
Duration of AF (Mean \pm SD, years) ¹	2.6 \pm 2.4
Medical History	N (%)
History of Smoking	21 (30)
Diabetes Mellitus Type II	8 (11.4)
Previous Stroke or TIA	6 (8.6)
Previous Myocardial Infarction	3 (4.3)
Coronary Artery Bypass Grafting (CABG)	0 (0)
Concurrent Medical Conditions	N (%)
Hepatic Disease	9 (12.9)
Pulmonary disease	17 (24.3)
Other Relevant Cardiac Diseases	N (%)
Hypertension	38 (54.3)
Hypertrophic Cardiomyopathy	0 (0)
Coronary Artery Disease	0 (0)

1 Onset date of PAF not collected in first phase subjects; data only available on 30 subjects.

Study Procedural Results

Pulmonary vein isolation (PVI) was achieved by point-by-point, wide antral ablation encircling each pair of ipsilateral PVs supported by the EnSite Velocity or Precision to collect electrical map of the atrium and assist the navigation of the DiamondTemp Catheter to each ablation site. The investigational device was used with the market-approved EnSite Velocity/Precision in 70/70 (100%) of the subjects. A summary of procedural data is listed in Table 4.

Table 4. Summary of Procedural Data, (N=70)

Procedure Data (n=70)	Measurement	Results
Mode of Operation	Temperature Control	

Programmed Infusion Rate (ml/min)	Standby Flow Rate – 2 ml/min Therapeutic Flow Rate – 8 ml/min		
No. of RF Applications [¥]	4662		
Ablation Duration [†] (sec)	Mean ± SD	17.5	± 2.4
	Range	10.2	- 22.4
Average Power [†] (W)	Mean ± SD	36.2	± 2.7
	Range	31.7	- 41.9
Max Power* (W)	Mean ± SD	50.8	± 0.5
	Range	50.2	- 53.1
Temperature Set-Point [†] (°C)	Mean ± SD	58.1	± 1.6
	Range	51.5	- 60
Max Temperature [†] (°C)	Mean ± SD	65.0	± 3.5
	Range	56.8	- 73.8
Average Temperature [†] (°C)	Mean ± SD	48.2	± 1.9
	Range	43.3	- 52.5
Max Impedance [†] (Ω)	Mean ± SD	134.7	± 31.2
	Range	94	- 239
Average Impedance [†] (Ω)	Mean ± SD	95.5	± 8.9
	Range	74.9	- 118.9
Total RF Ablation Time [†] (min)	Mean ± SD	19.8	± 8.6
	Range	8.5	- 41.8
Total Procedure Time (mean)	Mean ± SD	2:35	± 0:47
	Range	1:25	- 4:35
Total Fluoroscopy Time [‡] (mins)	Mean ± SD	9:38	± 6:38
	Range	0:03	- 18:00
Total fluid vol. [§] (ablation procedure)	Mean ± SD	322.6	± 99
	Range	152	- 531

¥ RF application count includes all ablations (PVI + atrial tachycardia, etc.)

† These values were generated from the generator, not the database.

‡ Fluoroscopic time not recorded on two subjects.

§ Fluid volume not collected on one subject.

Once electrical isolation was achieved, ablation in the targeted veins was considered complete. Documentation of entrance block into the PVs (PVI) was required for each vein ablated. PVI was confirmed by either testing with an adenosine bolus (n=36, 51% of subjects) or confirming PVI after a minimum of 20 minutes (n=34, 49% of subjects) after the last RF application.

Primary Endpoint Results

All primary study endpoints have been met through 30 days. Assessments of primary safety events resulted in a total of two (2) SAEs (2.9%) through the 7-day safety endpoint and three (3) SAEs (4.3%) through the 30-day safety endpoint, as adjudicated by an independent CEC (Table 5). The primary effectiveness endpoint of acute procedural success was achieved in 100% of subjects.

Table 5. Summary of Primary Safety Endpoint (Analyzable Population)

Event	DiamondTemp N=70	Timing
	Subjects (%)	
Pericardial Effusion	1 (1.4%)	Prior to 7 days
Hospitalization for AF recurrence	1 (1.4%)	Prior to 7 days
Supraventricular Tachycardia	1 (1.4%)	Prior to 30 days
Total SAEs through 7 days	2 (2.9%)	
Total SAEs through 30 days	3 (4.3%)	

Long Term Interim Safety Analysis

The chronic safety of the DiamondTemp Ablation System was assessed in TRAC-AF by evaluating the nature and frequency of all serious adverse events at 90 days, 6 months and 12 months post-procedure, as adjudicated by the CEC.

4.1.8 Conclusion from Clinical Study

The objective of the TRAC-AF First-In-Human study was to substantiate the safety and effectiveness of the DiamondTemp Ablation System to ablate cardiac tissue in patients with paroxysmal Atrial Fibrillation. The study endpoints achieved the efficacy performance goal demonstrating 100% effectiveness by confirming PVI in all subjects treated as intended under the study protocol. Freedom from AF 12 months post-procedure was 72.5%. The safety profile demonstrated in the study indicates the DiamondTemp Ablation System can be used safely in cardiac ablation procedures in the defined patient population, with no incidences of acute serious adverse device-related events (SADEs) and a 2.9% to 4.3% safety endpoint rate through 7 and 30 days, respectively.

The safety results observed in the subjects treated with the DiamondTemp Ablation System up to 30 days are well within the recommendations of the published literature and documented safety and efficacy rates of catheter ablation for PAF.^[10]

4.2 Purpose

The purpose of this study is to demonstrate the safety and effectiveness of the DiamondTemp Ablation System for the treatment of drug refractory, symptomatic persistent Atrial Fibrillation.

5. Endpoints**5.1 Primary Safety Endpoint**

The primary safety endpoint is defined as freedom from a composite of serious adverse events (SAEs) occurring within 7 days, procedure and/or device-related significant pericardial effusion that occurs within 30 days and severe or clinically symptomatic pulmonary vein stenosis and atrioesophageal fistula through 6 months post-index ablation procedure, as adjudicated by an independent Clinical Events Committee (CEC) for relatedness to the procedure or device.

The primary safety device- or procedure-related SAE composite will be the combined rate of the following events in Table 6.

Table 6. Primary SAE, Classification and Definition

Primary SAE	Severity Classification / Definition ^[10]
Atrioesophageal fistula	Creation of direct communication between the left atrium and esophagus as documented by esophageal erosion combined with evidence of a fistulous connection to the atrium (e.g. air emboli, an embolic event or direct observation at the time of surgical repair). A CT or MRI scan is recommended to document event.
Bleeding complication	Major bleed that requires a transfusion or results in a $\geq 20\%$ fall in hematocrit.
Cardiac tamponade / perforation	Significant pericardial effusion with hemodynamic compromise that requires elective or urgent pericardiocentesis or results in a 1-cm or more pericardial effusion as documented by echocardiography.
Death	Cardiovascular-related death post ablation that is related to the procedure or device.
Extended hospitalization	Extended hospital stay or re-hospitalization that is related to the procedure or device.*
Myocardial infarction	MI as it relates to AF ablation resulting in the presence of any one of the following criteria: 
 ECG changes indicative of new ischemia that persist for > 1 hour development of new pathological Q waves on an ECG imaging evidence of new loss of viable myocardium or new regional wall motion abnormality
Pericarditis	Pericarditis resulting in an effusion that leads to hemodynamic compromise, requires pericardiocentesis, prolongs hospitalization > 48 hours or persists for more than 30 days following procedure.
Phrenic nerve paralysis	Absence of phrenic nerve function assessed by a sniff test that persists > 7 days. A phrenic nerve paralysis is considered to be permanent when it is documented to be present ≥ 12 months following ablation.
Pulmonary edema	Pulmonary alveolar fluid accumulation accompanied by typical symptoms (dyspnea), physical findings (rales, hypoxemia), radiologic findings, and response to diuretic therapy and requiring or prolonging hospitalization.
Pulmonary vein stenosis	A severe or clinically symptomatic PV stenosis verified by a chest CT or MRI will be classified as a SAE. PV stenosis symptoms are shortness of breath, cough and hemoptysis. Pulmonary vein stenosis is defined as a reduction of the diameter of a PV or PV branch. PV stenosis will be categorized as mild $<50\%$, moderate 50%–70%, and severe $>70\%$ reduction in the diameter of the PV or PV branch when compared to the proximal reference diameter.
Significant Pericardial Effusion	Results in hemodynamic compromise, requires elective or urgent pericardiocentesis or results in a 1-cm or more pericardial effusion as documented by echocardiography.
Stroke/CVA	Stroke Diagnostic Criteria:

post-ablation	
Rapid onset of a focal or global neurological deficit with at least one of the following: change in level of consciousness, hemiplegia, hemiparesis, numbness or sensory loss affecting one side of the body, dysphasia or aphasia, hemianopia, amaurosis fugax or other neurological signs or symptoms consistent with stroke.
 
Duration of a focal or global neurological deficit ≥24 hours; or <24 hours if therapeutic intervention(s) were performed (e.g., thrombolytic therapy or intracranial angioplasty); or available neuroimaging documents a new hemorrhage or infarct; or the neurological deficit results in death
 
No other readily identifiable non-stroke cause for the clinical presentation (e.g., brain tumor, trauma, infection, hypoglycemia, peripheral lesion, pharmacological influences).[^]
 
Confirmation of the diagnosis by at least one of the following: neurology or neurosurgical specialist; neuroimaging procedure (MRI or CT scan or cerebral angiography); lumbar puncture (i.e., spinal fluid analysis diagnostic of intracranial hemorrhage.)
 
Stroke will be determined by the consulting neurologist using diagnosis criteria above and subsequent neuroimaging procedure (MRI or CT scan or cerebral angiography).
 
[^] Subjects with non-focal global encephalopathy will not be reported as a stroke without unequivocal evidence based on neuroimaging studies.

Thromboembolism	Occurrence of deep vein thrombosis or pulmonary embolism post ablation.
Transient ischemic attack (TIA) post-ablation	Rapid onset of new focal neurological deficit with immediate symptom resolution (usually 1 to 2 hours), always within 24 hours as determined by consulting neurologist and neuroimaging without tissue injury.
Vagal nerve injury	Esophageal dysmotility or gastroparesis requiring or prolonging hospitalization following an ablation procedure.
Vascular access complications	Resulting in development of a hematoma, an AV fistula or a pseudoaneurysm that requires intervention, such as surgical repair or transfusion, prolongs the hospital stay, or requires hospital admission.

*Planned hospitalization for a pre-existing condition, or a procedure required by the Clinical Investigational Plan (including repeat ablation procedure), without serious deterioration in health, will not be included in the primary safety endpoint analysis. Hospitalizations due to recurrent AF/AT/AFL or prolonged hospitalization during the 30 days following procedure to adjust anticoagulation or anti-arrhythmia regimen or to administer diuretic medication are not considered part of the combined primary safety endpoint.

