Table 12: Adverse Event Classification Responsibilities

What is classified?	Who classifies?	Classification Parameters
Relatedness	Investigator	Procedure related; device related
	Sponsor	Procedure related; device related
Seriousness	Investigator	SAE, Device Deficiency with SADE potential
	Sponsor	SAE, UADE/USADE, Device Deficiency with SADE potential
Diagnosis	Investigator	Based on presenting signs and symptoms and other supporting data
	Sponsor	MedDRA term assigned based on the data provided by Investigator
Cause of Death	Investigator	Cardiac, Non-Cardiac, Unknown

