E	
 Updated TRAC-AF study section (Section 5.5, Table 2 and Table 4) 	
 Updated section to include final study data results. 	N/A- historical revision from 14Mar2019.	N/A- historical revision from 14Mar2019.	[name]- EPIX Therapeutics
F	
Changes made in regards to Study Analysis and overall CIP Content:
 
 Updated study contact information. Removed “Death” definition within table of definitions. 	
 Changed to reflect primary Sponsor study contact Inaccurately defines Death as “Cardiovascular related death post ablation”. Removed for consistency within the CIP. 	N/A- All study documents updated according to the ISO14155:2020 Revision. Also merged from EPIX SOP's to MDT SOP's concurrently. None of the changes being made to the CIP impact the	N/A- All study documents updated according to the ISO14155:2020 Revision. Also merged from EPIX SOP's to MDT SOP's concurrently.	[name]-CRS

DIAMOND-AF II Clinical Investigation Plan

Version H

Page 99 of 111

Medtronic
Form

Version	Summary of changes	Justification of changes	Potential impact of the change on performance, effectiveness, or safety or other endpoints	Identification of the affected study documents	Author(s)/Title

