7.9.1 Primary Safety Objective

Primary Safety Objective

To demonstrate that the primary safety event rate associated with the DiamondTemp ablation system is lower than the pre-specified Objective Performance Criterion (OPC).

Hypothesis

 $H_0: P \geqslant P_0$

 $H_1: P < P_0$

where $P_0 = 11.5\%$ (Safety OPC), and lower event rates are better.

Endpoint Definition and Derivation

Revision 1 Page 9 of 18

The primary safety endpoint is defined as freedom from a composite of serious adverse events (SAEs) occurring within 7 days, procedure and/or device-related significant pericardial effusion that occurs within 30 days, and severe or clinically symptomatic pulmonary vein stenosis and atrioesophageal fistula through 6 months post-index ablation procedure, as adjudicated by an independent Clinical Events Committee (CEC) for relatedness to the procedure or device.

The primary safety device- or procedure-related SAE composite will be the combined rate of the following events:

- Atrioesophageal fistula
- Bleeding complication
- Cardiac tamponade / perforation
- Death
- Extended hospitalization
- Myocardial infarction
- Pericarditis
- Phrenic nerve paralysis
- Pulmonary edema
- Pulmonary vein stenosis
- Significant pericardial effusion
- Stroke / CVA
- Thromboembolism
- Transient ischemic attack (TIA)
- Vagal nerve injury
- Vascular access complications

Performance Requirements

The null hypothesis will be rejected if the one-sided 97.5% upper confidence bound of the primary safety event rate is lower than 11.5%.

Rationale for Performance Criteria

This performance goal was derived from a point estimate of 7% and a margin of indifference of 4.5%. This point estimate value was determined from a review of the FDA publicly available information combined with the published literature for all FDA approved medical device trials for Atrial Fibrillation treatment¹ and some other studies² on ablation treatment for Atrial Fibrillation. Based on the Sponsor's

Wilbur, et al. JAMA Vol. 303, No. 4. P333-340.

https://www.accessdata.fda.gov/cdrh docs/pdf3/P030031S011b.pdf https://www.accessdata.fda.gov/cdrh_docs/pdf15/P150026B.pdf Dukkipati, et al. JACC Vol 66. No.12, 2015. p1350-1360.

https://www.accessdata.fda.gov/cdrh_docs/pdf10/P100010b.pdf

[figure not shown]
Natale, et al. JACC Vol.64, No.7, 2014. P 647-656.

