7.10 Safety Evaluation

Adverse event classifications and definitions are described in the Clinical Investigational Plan.

An overall summary of adverse events will be presented to include the number and percentage of subjects who report at least one adverse event, the total number of adverse events, the number of adverse events and the number and percentage of subjects who report adverse events by seriousness and relationship to the study treatment (i.e., study ablation procedure or device). For events adjudicated by the CEC, the CEC classifications will be used in the analysis; in cases where only the investigator classifies the event, the investigator's classification will be used.

The frequencies and percentages of adverse events will be presented by MedDRA system organ class (SOC) and preferred term (PT). The frequencies and percentages of AEs judged to be at least possibly related to study treatment will be presented by MedDRA SOC and PT. Similar tables will be presented for the subset of serious adverse events (SAEs).

Complete subject listings of all adverse events, all SAEs, and all AEs at least possibly related to study treatment will be provided. For each adverse event the following details will be specified: start and stop dates, event description, MedDRA SOC and PT, relationship to study ablation device, relationship to study ablation procedure, actions taken, outcome of the adverse event and seriousness (yes/no).

A summary table of all deaths will be compiled to summarize death classification and relationship to study treatment. A detailed listing of all deaths will also be provided.

A detailed listing of all reported device deficiencies will be provided.

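### Table 6 limits the Death component of the primary safety endpoint to cardiovascular deaths, while the synopsis, Protocol 14.4.1 and SAP 7.9.1 list Death without any cause restriction

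*Protocol*

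**What the plan says.** Protocol 5.1 defines primary safety as "freedom from a composite of serious adverse events (SAEs) occurring within 7 days", with longer windows for significant pericardial effusion (30 days) and for pulmonary vein stenosis and atrioesophageal fistula (6 months). Events are adjudicated by the CEC for relatedness. The section then says: "The primary safety device- or procedure-related SAE composite will be the combined rate of the following events in Table 6". The Death row of that table reads: "Cardiovascular-related death post ablation that is related to the procedure or device".

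Three other places list the components: the synopsis, Protocol 14.4.1 and SAP 7.9.1. The SAP introduces its list with "The primary safety device- or procedure-related SAE composite will be the combined rate of the following events". In all three, Death stands alone, with no cause qualifier and no pointer to Table 6. For definitions, SAP 7.10 states: "Adverse event classifications and definitions are described in the Clinical Investigational Plan". Table 6 holds the only current definition of Death in the protocol.

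Two further passages bear on the point. Protocol Table 12 has the investigator classify cause of death as "Cardiac, Non-Cardiac, Unknown". The version F entry in the Version History (Protocol 21) explains why a Death entry was taken out of the table of definitions: "Inaccurately defines Death as “Cardiovascular related death post ablation".

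**The concern.** The composite already requires relatedness to the procedure or device. Table 6 adds a second condition, cardiovascular cause, which the other three lists do not carry. Protocol 11.1 names sepsis, pneumothorax and anesthetic reactions among the procedural risks. A related death from one of these could meet the unrestricted lists and fail Table 6, while a hematoma that prolongs the hospital stay counts in all of them.

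A death that is not an event does not remain in the analysis as a failure. Protocol 10.9 names death among the reasons for withdrawal, and SAP 7.4 censors subjects who discontinue without an endpoint event at their last study contact. The most serious related outcome could thus drop out of the numerator of a pivotal safety claim. Secondary objective 1 uses the same event types to 30 days (Protocol 14.5.1, SAP 7.9.3.1) and inherits the ambiguity. Settling the definition after such a death has occurred would look post hoc.

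**Working it through.** **Step 1. Set the definitions side by side.**

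| Place | Death component |
|---|---|
| Protocol 5.1, Table 6 | cardiovascular and related |
| Protocol synopsis | Death, related, no cause filter |
| Protocol 14.4.1 | Death, related, no cause filter |
| SAP 7.9.1 | Death, related, no cause filter |
| SAP 7.10 | refers to the protocol for definitions |

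The SAP's cross-reference leads back to Table 6, so the SAP does not remove the restriction.

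**Step 2. Find which deaths are affected.** A death falls in the gap only if all four conditions hold: it is within 7 days, it is adjudicated as related, it is not cardiovascular, and the subject had no other component event in that component's window.

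**Step 3. Reproduce the plan's figure.** Inputs from Protocol 14.7 and 14.4.1: n = 269, expected rate 7%, limit 11.5%, one-sided alpha 0.025, stated power 81%. With the variance taken at the expected rate, the standard error is √(0.07 × 0.93 / 269) = 0.01556, and power = Φ(0.045 / 0.01556 − 1.96) = 82.5%. This is within 2 points of the stated figure. It is background here, used only to fix n and the rates.

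**Step 4. Find the pass/fail boundary under the SAP's log-log bound.** Assume no censoring. With x events, S = 1 − x/n, the standard error on the log-log scale is √(S(1−S)/n) / |S log S|, and the upper bound for the event rate is 1 − exp(−exp[log(−log S) + 1.96 × SE]).

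- x = 20: rate 7.43%, log(−log S) = −2.5606, SE = 0.2237, upper bound 11.29%. Pass.
- x = 21: rate 7.81%, log(−log S) = −2.5098, SE = 0.2183, upper bound 11.72%. Fail.

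One event is worth 1/269 = 0.37 percentage points.

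**Step 5. How often could one death decide the result?** Only if exactly 20 other subjects have events. At the planned 7% rate, the binomial probability of exactly 20 in 269 is 8.9%. That must still be multiplied by the chance that such a death occurs, for which the documents give no figure.

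**Step 6. Effect on the chance of a false pass.** Let the true rate including these deaths be 11.5%, and let an assumed share go uncounted. The chance of 20 or fewer counted events in 269 is:

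| Uncounted share (assumed) | Chance of passing |
|---|---|
| 0 | 1.9% |
| 0.1 points | 2.1% |
| 0.2 points | 2.4% |
| 0.3 points | 2.6% |
| 0.5 points | 3.3% |

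**The case against.** The strongest reply is that very few deaths fall in the gap. The other components have no cardiovascular filter. Extended hospitalization covers any related prolonged stay or re-admission, subject to the exclusions under Table 6, and bleeding, stroke, thromboembolism and fistula count whatever the final cause of death. A fatal sepsis would often prolong the stay first and so already be an event. This stands, and it limits the point to related non-cardiovascular deaths with no other component.

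A reader might infer more than the documents support, in four ways.

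- *That deaths of unknown cause are excluded.* No text says so. There is simply no stated rule for them.
- *That the CEC and the analyst could score the same death differently.* SAP 7.10 makes the CEC classification govern for adjudicated events, so such a split is unlikely. Whether the CEC works from Table 6 is not shown either, because its charter is not among the documents.
- *That the categories in Table 12 make the definition unworkable.* Those are the investigator's categories. Protocol 12.5 also collects a detailed description, cause and relatedness, and allows hospital records, autopsy report and death certificate to be collected, from which the CEC can judge.
- *That the sponsor has already disowned the Table 6 row.* The version F entry concerns a glossary entry that is no longer in the text. The part it quotes lacks the relatedness clause of Table 6. The log describes superseded text and is at most suggestive.

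It is also fair that SAP 7.10 tabulates and lists every death, so an uncounted one would be visible in the report. But visibility in a listing does not put it into the primary estimate.

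**Conclusion.** The inconsistency is in the current text and should be corrected. Section 5.1 makes Table 6 the defining list, and followed as written it leaves out a related non-cardiovascular death in the 7-day window that is accompanied by no other component event. The direction is certain: the restriction can only reduce the count.

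The expected size is small. A reader might infer that every related death of other or unknown cause is scored as event-free, or that the primary result is materially biased. Neither follows, since many such deaths would count through another component and the false-pass chance moves only from 1.9% to between 2.1% and 3.3% over the assumed range of 0.1 to 0.5 points.

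The boundary of 20 against 21 events rests on n = 269 and no censoring. At an assumed 306 subjects (269 / 0.88, from the planned 12% drop-out) the limit is 24 events. The reason to act is the credibility of the safety claim, at almost no cost, rather than the arithmetic.

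**What to change.** Delete the cardiovascular qualifier from the Death row of Table 6, so that Death means any death in the window that the CEC adjudicates as related to the procedure or device. Repeat that definition in SAP 7.9.1, and carry it into the CEC charter so that all sources agree. Have the CEC adjudicate the relatedness of each death of unknown cause explicitly and record the decision. Counting such deaths by default would be a further design preference and is not needed to remove the inconsistency.

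The cost is one line in each document. No new data are collected and the sample size is unchanged. The downside is that the observed event rate may be very slightly higher.
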